3.0 STUDY POPULATION

A total of 60 adults with definite, probable, or possible TBM, aged 18 years or older from Masaka Regional Referral Hospital.

3.1 Inclusion criteria

- 1. Age > 18 years
- 2. Written informed consent from participant or proxy

3. Definite, probable, possible, or suspected TBM diagnosis wherein the patient is being committed to a full course of anti-TB treatment for TBM in the setting of routine care.

All participants must have at least one of the following signs/symptoms: headache, irritability, vomiting, fever, neck stiffness, convulsions, focal neurological deficits, altered consciousness, or lethargy. In addition, participants must have CSF glucose to plasma ratio < 0.5 **OR** positive CSF acid-fast bacilli (AFB) smear **OR** positive CSF GeneXpert or Xpert Ultra **OR** clinician intent to initiate TB treatment for suspected TB meningitis.

Definite, probable and possible TBM will be defined as:

Definite TBM is defined by the presence of one or more of the following⁴⁵:

- Acid- fast bacilli (AFB) seen in the CSF, *M tuberculosis* cultured from CSF, or a CSF *M tuberculosis*-positive nucleic acid amplification test (e.g., Gene Xpert Ultra) performed within 14 days of entry
- AFB seen in the context of histological changes consistent with tuberculosis in the brain with suggestive symptoms or signs and CSF changes.

Probable and possible TBM are defined using previously published consensus criteria as shown in Appendix A⁴⁵.

- Probable TBM is defined as a total score of ≥12 when neuroimaging is available or total score of ≥10 when neuroimaging is unavailable. At least two points should either come from CSF or cerebral imaging criteria.
- Possible TBM is defined as a total score of 6–11 when neuroimaging is available, or total score of 6–9 when neuroimaging is unavailable.

Exclusion of the most likely alternative diagnoses is also required (e.g., negative cryptococcal antigen). Because culture confirmation is rarely available or often delayed in TBM, patients with probable or possible TBM will be recruited based on these predefined criteria, and CSF will be collected for mycobacterial culture and molecular testing. Classification of participants as definite, probable, or possible TBM will be made retrospectively once all necessary data are available.

3.2 Exclusion criteria

- 1. >5 doses of TB treatment received within previous 5 days
- 2. Discontinued TB treatment in prior 14 days
- 3. Known current/previous drug resistant TB infection
- 4. Known allergy to RIF, INH, PZA, EMB, LZD
- 5. Previous treatment of TB or TBM with LZD

6. Concomitant or planned use of monoamine oxidase inhibitors, selective serotonin reuptake inhibitors, HIV protease inhibitors, or any other drug with significant interaction with RIF, LZD, or any TB drugs (see **Appendices C and D**)

7. Women who are pregnant or breastfeeding, or women or men of reproductive potential who are unwilling to use at least one reliable form of barrier contraception or to abstain from sexual activity while receiving study drug treatment and for 30 days after stopping study treatment. Acceptable forms of contraception include: condoms (male or female) with or without a spermicidal agent, or diaphragm or cervical cap with spermicide. Hormonal contraception is not recommended as it may be ineffective due to induction of metabolism when receiving rifampicin.

8. Unwillingness to be an inpatient for 2 weeks for initial treatment or to attend follow up clinic visits

9. Lack of informed consent from participant or next of kin/caregiver

10. Serum creatinine >1.8 times upper limit of normal, hemoglobin <7.0 g/dL for men, <6.5 g/dL for women, platelet count <50,000/mm³, absolute neutrophil count <600/mm³, alanine aminotransferase (ALT) >3 times the upper limit of normal, total bilirubin >2 times the upper limit of normal.

11. Severe peripheral neuropathy defined by Grade 3 symptoms AND vibratory loss OR absent ankle jerks for participants able to undergo the Brief Peripheral Neuropathy Screen (see Appendix B).

12. Contraindication to LP, including PLT <50 cells/mm³ or unequal pressures between intracranial compartments (e.g., due to mass lesion, non-communicating hydrocephalus), or unwillingness to undergo or consent to LP

3.3 Late exclusion (exclusion after enrollment)

1. Confirmed drug-resistant MTB infection: Resistance testing will be performed on all *M. tuberculosis* isolates from cerebrospinal fluid or other specimens obtained prior to randomization. If a participant is confirmed to have drug resistant infection, defined as resistance to one or more first-line TB medications or linezolid, they will be excluded from the study. If drug resistance is confirmed through phenotypic susceptibility testing, results may not become available until after a participant is enrolled, at which point they would meet criteria for late exclusion.

2. Identification of an alternative cause of meningitis: If CSF or other laboratory or pathology results return after a participant is enrolled indicating an alternative (or secondary) cause of meningitis, they would meet criteria for late exclusion.

Participants who meet criteria for late exclusion will discontinue study treatment but remain on study. These participants will be replaced in order to maintain a balanced number of participants per arm.

4.0 STUDY DESIGN

This is an open-label, randomized clinical trial with a factorial design. Initial randomization will be to high (35 mg/kg/day) versus standard (10 mg/kg/day) dose oral rifampin for the first 4 weeks of intensive therapy. Participants will then undergo a second randomization to linezolid 1200 mg daily versus no linezolid for the first 4 weeks of therapy. We will use a computer generated permuted block randomization (block size = 2 or 4) stratified by TBM grade (1 vs 2 and 3), given the association between TBM severity and mortality. The trial is open label, although we will endeavor for research staff assessing adverse events, neurocognitive and functional outcomes, and PK data to be blinded.

Initiation of high or standard dose oral rifampicin and linezolid or no linezolid will begin immediately (within 24 hours) after randomization. In addition, all participants will receive a standard backbone of oral TB treatment with INH 5 mg/kg/day, PZA 25 mg/kg/day, EMB 20 mg/kg/day, corticosteroids (IV dexamethasone 0.4 mg/kg/day for week 1, 0.3 mg/kg/day for week 2, followed by a prednisone taper over 6 weeks), and vitamin B₆ 50 mg daily. After the first 4 weeks of therapy, participants will receive standard dose oral RIF (10 mg/kg/day) for another 11 months along with standard treatment for TBM per national guidelines. Patients admitted to Masaka Regional Referral Hospital who meet eligibility criteria will be invited to participate.

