- **DESIGN** ALTER is a phase II randomized, open-label trial using a factorial design of high or standard dose rifampicin with or without linezolid for the first 4 weeks of treatment for tuberculous meningitis (TBM). Initial randomization will be to high (35 mg/kg/day) versus standard (10 mg/kg/day) dose oral rifampicin for 4 weeks. After randomization to high versus standard dose rifampicin, participants will undergo a second randomization to linezolid 1200 mg daily versus no linezolid for 4 weeks.
- DURATION 24 weeks
- SAMPLE SIZE 60 participants
- **POPULATION** Participants with definite, probable, or possible TBM, aged \geq 18 years
- SETTING Masaka Regional Referral Hospital, Masaka, Uganda
- **STRATIFICATION** Participants will be randomized with stratification by HIV status and stage of disease (Grade 1 vs. 2 and 3), as defined by the modified British Medical Research Council criteria.
- **REGIMEN** Participants will first be randomized 1:1 to:

High dose rifampicin 35 mg/kg for 4 weeks vs. standard dose rifampicin 10 mg/kg

Participants will then be randomized 1:1 to:

Linezolid 1200 mg daily for 4 weeks vs. no linezolid (see **Table 1**)

In addition, all participants will receive standard treatment for TBM with isoniazid 5 mg/kg/day, pyrazinamide 25 mg/kg/day, ethambutol 20 mg/kg/day, corticosteroids (IV dexamethasone 0.4 mg/kg/day for 1 week, 0.3 mg/kg/day for 1 week, followed by a prednisone taper over 6 weeks), and vitamin B₆ 50 mg daily. After the first 4 weeks of therapy, participants in the high dose rifampicin arm (Arm A) will receive standard dose oral rifampicin (10 mg/kg/day) for another 11 months as per national guidelines.

		RI	F
colid		High dose (35 mg/kg)	Standard dose (10 mg/kg)
inez	+	Arm A: R ₃₅ HZEL	Arm B: R ₁₀ HZEL
	-	Arm C: R ₃₅ HZE	Arm D: R ₁₀ HZE

 Table 1: Study regimens

R, rifampicin; H, isoniazid; Z, pyrazinamide; E, ethambutol; L, linezolid

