4.1.7 Randomization

At study entry and prior to the 4th dose of TB treatment, participants will first be randomized by a computer-generated permutated block randomization (block size of 2 or 4) with a 1:1 randomization to high (35 mg/kg) versus standard dose (10 mg/kg) rifampicin. A second 1:1 randomization will then be performed to linezolid 1200 mg daily or no linezolid. Randomization will be stratified by British Medical Research Council (BMRC) TBM disease grade (Table 2), determined at the time of consent, given the association between worse disease severity and higher mortality¹.

Table 2. British Medical Research Council (BMRC) TBM disease grade

GRADE I	Glasgow coma score 15, no focal neurological signs
GRADE II	Glasgow coma score 11–14 with or without focal neurological sign or Glasgow coma score 15 with focal neurological signs
GRADE III	Glasgow coma score \leq 10 with or without focal neurological signs

The randomization schedules will be provided to the site pharmacy in a listed sequence. The sequential, unique randomization code will be recorded on the study entry CRF to assure there is no

skipping of the randomization order. All randomized participants will initiate their allocated study TB treatment within 24 hours of randomization and ideally the same day. For participants from whom informed consent has been obtained, but who are deemed ineligible or who do not enroll into the protocol, a Screening Failure form must be completed and entered into the database.

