10.0 STATISTICAL CONSIDERATIONS

10.1 Sample size estimation

Sample size calculations for the PK analyses are based on different study designs (varying number of participants and time points) using clinical trial simulations. We used the stochastic simulationestimate "sse" methodology for clinical trial simulation and re-estimation to determine sample sizes required to evaluate key PK parameters with precision adequate to determine optimal dosing for a future efficacy trial of LZD. This methodology simulates the data from a planned trial with a proposed design (e.g., number of participants) followed by the estimation of the parameters under the true and alternative models. This is repeated a minimum of 1000 times to estimate PK parameters, standard errors and inter-individual variability. With 30 participants receiving LZD, we will be able to estimate PK parameters with required precision of relative standard errors <10% for typical values and <25% for random effects (inter-individual variability). For the evaluation of LZD adverse events, if we assume 40% of participants in the LZD arm and 10% in the no LZD arm will experience myelosuppression.^{78,84} the planned sample size of 60 participants (n=30 per arm) will provide at least 80% power to detect a similar or greater difference in the frequency of myelosuppression between arms at a significance level of 0.05. Given the modest sample size, we recognize that we may not have adequate power to compare the frequency of myelosuppression in participants on LZD and standard versus high dose RIF; however, if the frequency of myelosuppression in participants on LZD and high dose RIF (n=20) is anticipated as \sim 25%, the 90% confidence interval of this estimate is 10% to 46% with a precision of 18%.

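### Block sizes of 2 or 4 are published for an open-label single-site trial, concealment from enrolling staff is not described, and the link between the two randomisations is not stated

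*Combined protocol and SAP*

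**What the plan says.** Section 4.0 specifies "computer generated permuted block randomization (block size = 2 or 4"), with strata formed by TBM grade (Grade 1 against Grades 2 and 3 together). Section 4.1.7 attaches the same block sizes to the first step, a "permutated block randomization (block size of 2 or 4) with a 1:1 randomization to high (35 mg/kg) versus standard dose (10 mg/kg) rifampicin", and continues: "A second 1:1 randomization will then be performed to linezolid 1200 mg daily or no linezolid". No block size is repeated for that second step, and nothing says whether it is run separately within each rifampicin arm.

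On custody of the sequence, section 4.1.7 says: "The randomization schedules will be provided to the site pharmacy in a listed sequence". A sequential code is entered on the study entry form to prevent skipping. How the people who identify and enrol patients are kept from the upcoming allocation is not described.

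On blinding, section 4.0 says: "The trial is open label, although we will endeavor for research staff assessing adverse events, neurocognitive and functional outcomes, and PK data to be blinded".

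The number of strata is also unsettled. The synopsis says: "Participants will be randomized with stratification by HIV status and stage of disease (Grade 1 vs. 2 and 3"), which makes four strata. Sections 4.0 and 4.1.7 name grade only, which makes two.

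**The concern.** Two things are at stake.

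**Predictability.** In an open-label single-site trial, staff see which regimen earlier participants received. With small blocks of known size, past allocations say a good deal about the next one. Entry leaves room for judgement: clinician intent to treat can satisfy the entry criterion in section 3.1, and enrolment timing depends on when a provisional diagnosis is made (section 4.1.3). If a guess influences who enters and when, the adverse event, functional and cognitive comparisons can be biased. Blinded assessment, which is only attempted, does not undo selection at entry.

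**Cell size.** The hypothesis in section 2.0 compares linezolid exposure with high and standard dose rifampicin, that is, arm A with arm B. Two blocked lists that take no account of each other balance each factor but leave the four cells free to drift. Section 3.3 shows that balanced arms are wanted, since late exclusions are replaced for that purpose.

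**Working it through.** **1. The plan's own figure.** No figure is given for predictability or cell balance. The nearest is in section 10.1: "the planned sample size of 60 participants (n=30 per arm) will provide at least 80% power", for 40% versus 10% myelosuppression at 0.05 (taken as two-sided).
- Unpooled normal formula: 0.3·√30 / √(0.24 + 0.09) − 1.96 = 1.643/0.574 − 1.96 = 0.90, power 81.6%.
- Arcsine 80.3%, exact chi-square 79.6%, pooled 78.0%.

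The claim reproduces with the first two. It depends only on the linezolid totals, which stay at 29–31 (1st to 99th percentile) under unlinked lists with two strata, so it is not threatened here.

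**2. Guessing one factor, by arithmetic.** The guesser names the arm with more places left in the block. Expected correct guesses per complete block:
- Block of 2: 1/2 + 1 = 1.5.
- Block of 4: 1/2 + 2/3 + 2/3 + 1 = 2.83.
- The two sizes equally often: (1.5 + 2.83)/6 = 72%.

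Allocations certain in advance to someone who knows the *current* block size are 1/2 in blocks of 2 and (4/3)/4 = 33% in blocks of 4.

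**3. Simulation of the whole design.** Inputs from the documents: 60 participants, blocks of 2 or 4, grade strata. Assumptions not in the documents: block sizes equally likely; 30% in Grade 1 (50% as a check); 60% with HIV where four strata are used. The guesser sees all earlier allocations in the stratum, knows the set of sizes, and guesses before either allocation is known. There were 600–800 replicates per design, with Monte Carlo error up to about 2 points on the balance probabilities.

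Two grade strata:

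| | Unlinked lists, 2/4 | Linezolid within rifampicin arm, 2/4 | One four-arm list, 4/8 |
|---|---|---|---|
| Correct guess, linezolid | 72% | 67% | 67% |
| Correct guess, rifampicin | 72% | 72% | 67% |
| Correct guess, full arm (chance 25%) | 54% | 52% | 47% |
| Full arm certain, only the set of sizes known | 1% | 1% | 7% |
| Full arm certain, current size known | 22% | 14% | 17% |
| SD of cell size | 2.2 | 0.7 | 0.7 |
| All four cells within 14–16 | 38% | 97% | 96% |
| All four cells exactly 15 | 7% | 27% | 27% |

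Under unlinked lists some cell has 12 or fewer in 32% of trials. With 50% in Grade 1 the unlinked result is unchanged (SD 2.2, 38% within 14–16) and the four-arm list gives 93%. With four strata, the chance that all cells are within 14–16 is 34%, 74% and 70% for the three designs, with SD 2.3, 0.9 and 0.9.

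**4. Cost of an uneven split.** With 30 linezolid participants split a and b, efficiency for A versus B relative to 15/15 is 4ab/900:
- 12/18: 864/900 = 96%.
- 10/20: 800/900 = 89%.

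**The case against.** The best defence has four parts.

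- **Safeguards exist.** The schedules sit in the pharmacy, skipping is checked, consent precedes randomisation (section 4.1.2), and randomisation must come before the fourth dose of TB treatment, which limits waiting for a preferred slot. This stands as mitigation. Calling the lists themselves open would be wrong: the trial is open label, and access to the sequence is simply not described. Nor do the documents show that staff track allocations by stratum.
- **Unlinked lists are an inference.** A reader might conclude that the four cells will drift. The documents do not say so. If linezolid is blocked within rifampicin arm, a four-arm list brings no better balance (96% versus 97% within 14–16) and no gain in guessing linezolid. This stands; the defect is the missing statement.
- **Certainty is easily overstated.** A reader might infer that a third to a half of allocations are known in advance. That requires knowing the current block size, and the plan mixes two. A guesser who knows only the set of sizes is certain of the full arm about 1% of the time now and 6–7% under the four-arm 4/8 list. Even with the current size known, certainty falls only against unlinked lists (22% to 17%); against nested lists it rises (14% to 17%). This is a real drawback of the change and the reason the sizes must be withheld.
- **The precision loss is small.** The primary analysis is one mixed-effects model of all concentrations (section 10.2), and step 4 shows the A versus B contrast tolerates moderate imbalance. This also stands.

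**Conclusion.** The point holds as a minor, inexpensive design improvement. Publishing blocks of 2 or 4 in an open-label single-site protocol, with no described concealment from enrolling staff, lets a well-informed guesser reach about 72% for rifampicin on either reading, 72% or 67% for linezolid, and 52–54% for the full arm. A four-arm 4/8 list lowers full-arm guessing by 4–7 points and rifampicin guessing by 4–5. It lowers linezolid guessing by about 5 points only if the lists would otherwise be unlinked.

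The cell-balance part is conditional. It matters if the lists are unlinked and disappears if linezolid is blocked within rifampicin arm. A reader might take a four-arm list to secure 15 per cell. It does not, because strata end in incomplete blocks: all cells are exactly 15 in 27% of trials with two strata and 8% with four. The figure of 15 is itself only 60/4; the plan never states it.

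These results rest on equal use of the block sizes, the assumed grade and HIV shares, and a guesser who follows every earlier allocation. They bound what is possible and are not evidence that selection will occur.

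**What to change.** In sections 4.0 and 4.1.7:

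1. Replace the two successive randomisations with one stratified four-arm list using randomly mixed blocks larger than 2, for example 4 and 8. Alternatively, state that linezolid is blocked within rifampicin arm, with larger varied blocks; that variant is not in the table above, and larger blocks inside smaller groups will loosen cell balance somewhat.
2. Remove the block sizes from the protocol and hold them in a restricted randomisation document.
3. State who holds the sequence and how each allocation is released only after a participant is irrevocably entered, so that enrolling staff cannot see it beforehand.
4. In the same edit, settle whether HIV status is a stratification factor (synopsis versus sections 4.0 and 4.1.7), and reconcile the n=20 that section 10.1 gives for linezolid with high dose rifampicin with 60/4 = 15.

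The cost is regenerating the list before enrolment and editing two sections. With the four-arm list, factor totals are slightly looser: the linezolid total ranges over 28–32 with two strata, or 27–33 with four, instead of 29–31. The effect on power is about a point: exact chi-square power is 78.8% at 32/28 (linezolid/no linezolid) and 80.3% at 28/32, against 79.6% at 30/30.

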4.1 Study enrollment procedures

Prior to implementation of this protocol, and any subsequent amendments, sites must have the protocol and the protocol consent form approved by their local institutional review board (IRB)/ethics committee and any other applicable regulatory entity. Site-specific informed consent forms must also be reviewed and approved by the local IRB/ethics committee. Once a candidate for study entry has

been identified, details will be carefully discussed with the participant. The participant (or, when necessary, the next of kin/caregiver if the participant lacks capacity to provide consent) will be asked to read and sign the approved protocol consent form. Participants from whom a signed informed consent has been obtained may be screened and enrolled, if they otherwise qualify. Participants who are enrolled through a next of kin/caregiver will provide consent once they regain capacity to consent.

4.1.1. Identification of participants and screening

Patients presenting to Masaka Regional Referral Hospital with suspected TBM will be identified by ward doctors. As part of routine clinical care they will undergo HIV test and lumbar puncture (LP), which can be done by the ward medical team or by the study team.

- In most cases, the ward medical team will perform the initial LP as part of routine care.
 However, study personnel can also perform the LP, if needed. If the participant has undergone a diagnostic LP as part of routine care, a repeat LP for screening is not necessarily required.
- If the LP has already been performed as part of routine care, after consent has been obtained, study personnel will facilitate the necessary diagnostic testing of the previously collected CSF.
- If persons are referred from outside health care facilities with appropriate documentation of TBM per study inclusion criteria, they will be eligible; however these persons must have a LP with a full diagnostic CSF analysis performed at the site approved laboratory after study consent is obtained to exclude alternative diagnoses.
- Screening evaluations, which can be performed as part of routine care, are outlined in the Schedule of Evaluations (Table 5)

Additional consent will be sought for long-term storage of samples, including blood and CSF. In this case, samples will be stored indefinitely, unless the participant asks for them to be destroyed. Participants may also give limited consent to the collection and testing of samples for the purposes of this research only, after which the samples will be destroyed.

